#### 4.6. Secondary Endpoint Analysis

There are no predefined secondary endpoints.

#### 4.7. Supportive Effectiveness Analysis

##### 4.7.1. Definition of Endpoints

**Subject Assessment Questionnaire**: The supportive effectiveness endpoints are based on each question of the Subject Assessment Questionnaire. At the Exit visit, subjects will report their level of agreement with each of a series of twelve statements in the Subject Assessment Questionnaire. Responses will be on a scale of one (strongly disagree) through six (strongly agree). These values will be dichotomized for analysis, with responses of one through three being mapped to the category of “Disagree” and responses of four through six being mapped to “Agree.”

##### 4.7.2. Analytical Approach

For each statement, the proportion of subjects who “Agree” with the statement will be determined for Test and Control. Statistical testing will proceed in two hierarchical families of twelve statistical tests each (one test per statement), with the null hypotheses of the first family eligible for rejection if all the primary endpoints are met.

- The first family will employ a one-sided exact binomial test to compare the proportion of respondents in the Test group agreeing with each statement to 0.5.
- The second family will employ a one-sided chi-square test to compare the proportion of respondents agreeing with each statement between the treatment groups.

Within each family of hypothesis tests, the  $P$ -values will be adjusted for multiplicity using the Holm method; specifically, the raw (i.e. unadjusted) one-sided  $P$ -values will be adjusted using SAS PROC MULTTEST with the Holm option. Adjusted one-sided  $P$ -values less than 0.025 will show statistical significance. The second family will only be analyzed for significance if the entirety of the first family is statistically significant. This gatekeeping strategy will preserve the overall type I error rate of 0.025 across both families.

The responses to each statement will be summarized categorically by treatment group in a table for the ITT Set. The adjusted  $P$ -values from the statistical tests will also be displayed along with an indicator of statistical significance. If the statistical tests in a family are not eligible for rejection due to hierarchy, then the adjusted  $P$ -values for that family will not be displayed.

## 4.8. Other Safety Analyses

### 4.8.1. Adverse Events

AEs will be collected from the day the subject gives informed consent until the subject withdraws (or completes) the study. All AEs will be followed until the event resolves or stabilizes (which may result in follow-up continuing after the subject has left the study). Investigators will assess whether each AE is related to study device (study solution) and/or rewetting drops using the categories not related or related, as well as the severity of each AE -- using the categories mild, moderate, severe.

Unless specified otherwise summaries of AEs will be presented in two ways, (1) counts (percentages) of subjects using the Safety Population, including all ocular and non-ocular AEs and (2) counts (percentages) of eyes using the Safety Population, including only ocular AE. The number of events will be reported as appropriate.

Summaries will be based on the coded system organ class (SOC) and preferred term (PT) using the latest MedDRA dictionary. The summaries will display the SOC in alphabetical order, while PTs within the SOC will be presented in order of overall decreasing frequency of occurrence in the Test arm. A subject/eye with multiple AEs (different PTs) coded to the same SOC will be counted only once for that SOC, but will be counted each time for the different PTs within that SOC. A subject/eye with separate events of the same PT (different start/stop dates) will be counted only once in the frequency tables for that PT.

A summary overview of AEs will be provided that gives the number of subjects/eyes with

- Any AE
- Any Treatment-Emergent AE (TEAE)
- Any Related (Study Solution or Rewetting Drops) TEAE
  - Any Related (Study Solution) TEAE
  - Any Related (Rewetting Drops) TEAE
- Any Severe TEAE
  
- Any Serious TEAE
- Any Related (Study Solution or Rewetting Drops) Serious TEAE
  - Any Related (Study Solution) Serious TEAE
  - Any Related (Rewetting Drops) Serious TEAE
  
- Any Non-Serious AE occurring in  $\geq 1\%$ ,  $\geq 2\%$ ,  $\geq 3\%$ ,  $\geq 4\%$ ,  $\geq 5\%$  subjects/eyes
  
- Any Significant Non-Serious TEAE
- Any Non-Significant Non-Serious TEAE
  
- Any Adverse Device Effect
- Any Severe Adverse Device Effect
- Any Unanticipated Serious Adverse Device Effect
  - Any Severe Unanticipated Serious Adverse Device Effect

- Any Anticipated Serious Adverse Device Effect
  - Any Severe Anticipated Serious Adverse Device Effect

All information pertaining to AEs noted during the study will be listed by subject/eye, detailing verbatim given the Investigator, PT, SOC, start date, stop date, severity, action taken, and device relatedness. The AE onset will also be shown relative (in number of days) to the day of initial use of the randomized study device.

No statistical testing will be performed for comparisons of AEs.

#### **4.8.1.1. Treatment Emergent Adverse Events**

Those AEs that emerge or worsen on or after Day 1, i.e., treatment emergent adverse events (TEAEs), will be the primary type of AEs reported in the CSR. Determination whether an AE emerged or worsened will be based on the coded lower-level term (LLT) from MedDRA.

For AEs with incomplete start or stop dates, the following rules will be used to impute start and/or stop dates for the sole purpose of determining if an AE is treatment emergent. Both the recorded partial dates and the associated imputed dates will be saved in the database.

- For partial stop dates, the latest possible date per the provided information will be used as the imputed AE stop date subject to the provision that the imputed AE stop date is not later than the subject's date of study completion or withdrawal.
- For partial start dates:
  - If the complete AE stop date, even if imputed, is prior to the date of Day 1, the imputed AE start date will be the complete AE stop date, and the AE is not treatment emergent.
  - Else if the month and year of AE onset/worsening are provided but day is missing, then
    - If the month and year match the month and year of Day 1, then the date when study intervention is first administered will be the imputed AE start date, and the AE will be considered treatment emergent.
    - Otherwise, the first day of the month provided will be the imputed AE start date, and treatment emergent status will be assessed relative to the date of Day 1.
  - Else if the year of AE onset is provided, but the month and day are missing
    - If the year matches the year of Day 1, then the date of Day 1 will be the imputed AE start date, and the event will be classified as treatment emergent.
    - Otherwise, January 1st for the provided year will be the imputed AE start date, and treatment emergent status will be assessed relative to the date of Day 1.
  - If the AE start date is completely missing, then the date of Day 1 will be the imputed AE start date., and the event will be classified as treatment emergent.

Events with missing relationship to study device will be considered related for statistical summaries, and events with unrecorded severity will be considered severe for statistical summaries. Any preferred terms with a missing relationship or severity will be described in the table footnotes.

#### 4.8.1.2. Treatment-Related TEAE

All AEs will be determined as either related or not related:

**Related:** There is at least a reasonable possibility that the AE is related to the study device (study solution) and/or rewetting drops. Reasonable possibility means that there is evidence to suggest a causal relationship or association between the study device and/or rewetting drops and the AE.

**Not related:** There is little or no reasonable possibility that the AE is related to the study device (study solution) and/or rewetting drops. This assessment implies that the AE has no evidence to suggest either a causal relationship or association to the study device and/or rewetting drops and a more likely or certain alternative etiology exists.

A summary of related TEAEs will be provided by relationship to (1) study device, (2) rewetting drops, or (3) both study device and rewetting drops.

#### 4.8.1.3. Serious Treatment-Emergent Adverse Events

An SAE is an AE that (related or not related to the investigational test articles, comparator products or study procedures):

- Led to death
- Led to serious deterioration in the health of the subject, that resulted in:
  - A life-threatening illness or injury; or
  - A permanent impairment of a body structure or a body function (e.g., blindness); or
  - Inpatient or prolonged hospitalization; or
  - Medical or surgical intervention to prevent life-threatening illness or injury or permanent impairment to a body structure or a body function
- Led to fetal distress, fetal death, or a congenital abnormality or birth defect.

*Note: A planned hospitalization for a pre-existing condition, or a procedure required by the protocol, without serious deterioration in health, is not considered an SAE.*

Serious adverse events may include but are not limited to any hazardous, sight-threatening conditions occurring after exposure to the investigational test article or control product including, but not limited to, the following:

- A presumed infectious ulcer (defined as a progressive erosion of the corneal tissue). For the purposes of reporting, this includes:
  - Central or para-central location
  - Penetration of Bowman's membrane
  - Infiltrate  $\geq 2$  mm diameter
  - Associated with iritis

- Associated with any increase in intraocular pressure
- Culture positive for microorganisms
- Increasing size or severity at subsequent visits

*NOTE: Signs of a presumed infectious corneal ulcer may include irregular focal infiltrates, active lesions with raised edges, significant diffuse infiltration, anterior corneal to mid-stromal involvement, erosion with overlying staining, conjunctival and lid edema, anterior chamber reaction (iritis), and severe bulbar and limbal redness. Symptoms associated with a presumed infectious ulcer (microbial keratitis) may include pain of rapid onset, severe redness, purulent or mucopurulent discharge, tearing, and photophobia.*

- Any central or paracentral (within the central 6 mm of cornea) corneal event that results in permanent opacification (such as corneal scar or vascularization)
- Any serious adverse ophthalmic events including hypopyon and/or hyphema
- Any neovascularization within the central 6 mm of the cornea
- Permanent loss of  $\geq 2$  lines of BSCVA
- All cases of iritis.

All SAEs will be listed. A summary of SAEs by SOC and PT will be provided.

#### **4.8.1.4. TEAE Resulting in Death**

Any TEAEs resulting in death will be included in the listing of SAEs and clearly marked as such.

#### **4.8.1.5. TEAE Leading to Study Treatment Discontinuation**

For every AE the investigator will indicate if the subject discontinued from the study due to the AE. A listing of all such subjects/eyes, along with their TEAE information, will be provided.

#### **4.8.1.6. TEAE by Maximal Severity**

A summary of TEAEs by maximal severity will be provided, where severity is either mild, moderate, or severe:

**Mild:** Subject awareness of a sign or symptom that is easily tolerated, requires no treatment, and does not interfere with subject's daily activities.

**Moderate:** Subject awareness of a sign or symptom which may be a low level of concern to the subject and may interfere with daily activities but can be relieved by simple therapeutic care.

**Severe:** A sign or symptom that interrupts the subject's daily activity and requires systemic therapy or other treatment.

#### **4.8.1.7. Significant Non-Serious TEAEs**

A summary of significant non-serious TEAEs will be provided. A significant non-serious adverse event is an AE that does not meet the serious criteria, is considered significant by the Sponsor, and requires expedited reporting to the Sponsor. These events include but are not limited to:

- Peripheral non-progressive non-infectious corneal ulcers.
- All symptomatic corneal infiltrative events.
- All cases of corneal staining greater than or equal to Grade 3.
- A temporary loss of two or more lines of BSCVA (for greater than or equal to 2 weeks).
- Neovascularization cases Grade 2 or greater (if not within 6 mm of the cornea).
- Any ocular event that necessitates temporary lens discontinuation of greater than or equal to 2 weeks.

#### **4.8.1.8. Non-Significant Non-Serious TEAEs**

A summary of non-significant non-serious TEAEs will be provided. A non-significant non-serious adverse event may include but are not limited to the following and does not require expedited reporting:

- Bacterial Conjunctivitis.
- Viral Conjunctivitis.
- Allergic Conjunctivitis.
- Corneal Edema.
- Contact Lens Related Papillary Conjunctivitis.
- Loss of Contrast Sensitivity.

#### **4.8.1.9. Additional Summaries of TEAEs**

Additional summaries of TEAEs will be provided:

- Related SAEs by relationship to (1) study device, (2) rewetting drops, or (3) both study device and rewetting drops.
- Severe TEAEs.
- TEAEs that are considered Adverse Device Effects.
- Serious TEAEs that are considered Adverse Device Effects by (un)anticipated status.
- Non-serious TEAEs occurring in 1% or more, 2% or more, 3% or more, 4% or more, and 5% or more of subjects/eyes

#### **4.8.2. Trend Analysis Profile**

For each treatment arm, a Trend Analysis Profile will be created to assist in the identification of trends, as per FDA guidance for contact lens care products. This will include summaries of the following, for each scheduled visit individually and overall:

- Total # of eyes (active or discontinued)
- Number of discontinued eyes
- Average wear time
- Number of lens replacements
- Number of total TEAEs
- Number of corneal ulcers
- Number of iritis episodes
- Corneal staining reports:

- Total number
- Total > Grade 2
- Total # of eyes
- Edema reports (for each of epithelial edema and epithelial microcysts):
  - Total number
  - Total > Grade 2
  - Total # of eyes
- Injection reports (for each of limbal and bulbar injections):
  - Total number
  - Total > Grade 2
  - Total # of eyes
- Upper lid tarsal conjunctival abnormalities reports:
  - Total number
  - Total > Grade 2
  - Total # of eyes
- Corneal neovascularization reports:
  - Total number
  - Total > Grade 2
  - Total # of eyes
- Corneal infiltrates reports:
  - Total number
  - Total > Grade 2
  - Total # of eyes
- Total visits
- Total missed visits

For mapping purposes, and for accounting for unscheduled events, the following assignments will be used, which maps a given day to its closest visit:

Visit	Target	Mapping Unscheduled Visits
2-Week Follow-up Visit	14 Days	0 – 22 Days
1-Month Follow-up Visit	30 Days	23 – 45 Days
2-Month Follow-up Visit	60 Days	46 - 75 Days
3-Month Follow-up Visit	90 Days	76 or more Days

The number of corneal ulcers and number of iritis are a subset of TEAE, which will be identified by qualified study personnel. The number of staining, edema, injection, and neovascularization reports come from the slit-lamp examination (note edema and injection both have two reports each per slit-lamp examination).

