- For each eye, compare the distance lens VA to the distance lens VA obtained at the Screening / Dispensing visit. If the VA has decreased by 10 letters (0.2 logMAR) or more, provide an explanation.
- Over-refraction and distance VA
- Lens wettability
- Lens deposits (type, percent and degree)
- Lens centration
- Lens movement
- f. Perform a slit-lamp examination (remove and store the lenses if the subject wore lenses to the visit). A lens case must be filled with *Bausch + Lomb Sensitive Eyes*[®] *Saline Solution* (NOT dispensed study solution) for storage of subject's lenses during the exam. If a corneal infiltrate is noted record details according to Corneal Infiltrates, Section 2.0: Slit-Lamp Examination of Appendix B: Methods of Clinical Evaluation.
- g. Record and sketch any scars and slit-lamp findings greater than Grade 2 in the subject's source document.
- h. Return the lenses to the subject to wear until the next study visit.
- i. If an unscheduled lens replacement is required, dispense a new pair of the subject's habitual contact lenses and go to Unscheduled Visits Section 6.1.6.
- j. Complete the following visit eCRFs:
 - 2-Week Follow-up Visit
 - Exit Visit (to be completed if the subject is discontinued or exited at this visit)
 - Collect Adverse Events

6.1.3 1-Month and 2-Month Follow-up Visits

The 1-Month and 2-Month Follow-up Visits will proceed as follows:

- a. If a subject misses either the 1-Month or 2-Month scheduled follow-up visit and cannot be seen prior to the start of the visit window for the next scheduled follow-up visit, then the visit is considered missed.
- b. Collect the following lens wear parameters from the subject:
 - Average daily wearing time (since last visit)
 - Average hours of comfortable wear (since last visit)
 - Hours lenses worn on the day of this visit
 - Did subject replace their lenses? (If so, when)
- c. Complete the Symptoms/Complaints Form (Study Lenses Symptoms/Complaints Rating Scales)
- d. Have the subject complete and initial the Lens Performance Assessment Form. (Study Lenses Performance Rating Scales, including use of rewetting drops.)
- e. Collect any relevant medical treatment information including any adverse events, including whether a culture may have been taken.

f. If the subject did not come to the visit wearing one or more study lenses, go to Step g. Otherwise, evaluate the lenses (while on eye):

NOTE: *All VA measurements MUST be made using a phoropter.*

- distance lens VA

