- For each eye, compare the distance lens VA obtained at the Screening / Dispensing visit with the distance lens VA obtained at this visit. If the VA has decreased by 10 letters (0.2 logMAR) or more, provide an explanation.
- Over-refraction and distance VA
- Lens wettability
- Lens deposits (type, percent, and degree)
- Lens centration
- Lens movement
- g. Perform a slit-lamp examination (remove the lenses if the subject wore lenses to the visit). Record and sketch any scars and slit-lamp findings greater than Grade 2 in the subject's source document. If a corneal infiltrate is noted record details according to Corneal Infiltrates, Section 2.0: Slit-Lamp Examination of Appendix B: Methods of Clinical Evaluation.
- h. Unmasked designee to collect the worn lenses from the subject. All worn lenses will be returned to the Sponsor in lens cases filled with Bausch + Lomb Sensitive Eyes® *Saline Solution* at the end of the study. Place the lens case in a labeled zippered bag.
- i. Unmasked designee to collect used Study Kit (bottle and carton) dispensed at the subject's previous visit.
- j. Unmasked designee to place the lens case in the labeled zippered bag and the used Study Kit (bottle and carton) in subject's bag. DO NOT seal subject bags until there is a full accountability by a Clinical Monitor at the end of the study.
- k. Dispense a new pair of subject's habitual lenses, instruct the subject to insert the lenses, and record the following information:

- Dispensed lens type (brand), sphere power, base curve
- distance lens VA
- For each eye, compare the distance lens VA obtained at the Screening / Dispensing visit with the distance lens VA obtained at this visit. If the VA has decreased by 10 letters (0.2 logMAR) or more, provide an explanation
- Over-refraction and distance VA
- Lens wettability
- Lens centration
- Lens movement
- 1. Unmasked designee to dispense a new Study Kit through the RTSM system, and record in the subject's individual Product Accountability Log. If needed, dispense any other supplies.
- m. Complete the following visit eCRFs:
 - 1-Month or 2-Month Follow-Up Visit

- Exit Visit (to be completed if subject is discontinued at this visit)
- Collect Adverse Events

6.1.4 **3-Month Follow-up**

The 3-Month Follow-up will proceed as follows:

NOTE: All VA measurements MUST be made using a phoropter.

- a. Collect the following lens wear parameters from the subject:
 - Average daily wearing time (since last visit)

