2.0 Slit-Lamp Examination

The following parameters will be assessed during the Slit-Lamp Examination (without lenses):

Epithelial Edema

- 0 None: No epithelial or sub-epithelial haziness. Normal transparency.
- 1 Trace: Barely discernible localized epithelial or sub-epithelial haziness.
- 2 Mild: Faint but definite localized or generalized epithelial haziness.
- 3 Moderate: Significant localized or general epithelial haziness.
- 4 Severe: Definite widespread, epithelial cloudiness giving dull glass appearance to cornea, or numerous coalescent bullae.

Epithelial Microcysts

- 0 None: no microcysts; normal transparency.
- 1 Trace: 1 to 20 microcysts; barely discernible local epithelial haziness.
- 2 Mild: 21 to 50 microcysts; faint but definite localized generalized haziness.
- 3 Moderate: 51 to 100 microcysts; significant localized or generalized haziness.
- 4 Severe: > 100 microcysts; definite widespread epithelial cloudiness giving a dull glass appearance to the cornea or numerous coalescing bullae.

Stromal Edema

- 0 None: no oedema.
- 1 Trace: just detectable clouding.
- 2 Mild: faint corneal striae (2 or fewer).
- 3 Moderate: pronounced corneal striae (3).
- 4 Severe: folds in Descemet's membrane pronounced striae.

Endothelial regularity

- 0 None: regular endothelial mosaic.
- 1 Minimal: isolated difference in cell size.
- 2 Mild: just noticeable variation in cell size or bumpiness of cell layer.
- 3 Moderate: easily detected difference in cell size or bumpiness of cell layer.
- 4 Severe: noticeable cell layer bumpiness and loss of definition of cell borders.

Corneal Staining

Corneal staining must be assessed after the instillation of fluorescein. A Wratten Gel Filter will be provided by the Sponsor for the evaluation of corneal staining. The Wratten Gel Filter must be used as a barrier filter in the observation pathway, in combination with the cobalt blue filter.

- 0 None: No fluorescein staining.
- 1 Trace: Minimal superficial staining or stippling, and non-coalescing. Includes superficial foreign body staining.
- 2 Mild: Lightly coalescent or diffuse punctate staining, with no stain diffusion into stroma.
- 3 Moderate: Significant or densely coalescent punctate staining, including slight diffusion of stain into stroma.
- 4 Severe: Severe abrasion or erosion with loss of epithelial substance. Marked and rapid diffusion of stain into stroma.

Limbal Injection

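### The Trend Analysis Profile's edema block (SAP 4.8.2) has no line for stromal edema, although the protocol grades it on its own 0–4 scale

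*SAP*

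**What the plan says.** SAP 4.8.2 sets up a Trend Analysis Profile for each arm, by scheduled visit and overall, to help identify trends. It cites FDA guidance for contact lens care products as its basis. One block is "Edema reports (for each of epithelial edema and epithelial microcysts"), with rows for the total number, the total above Grade 2 and the number of eyes.

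The closing text of 4.8.2 gives the source: "The number of staining, edema, injection, and neovascularization reports come from the slit-lamp examination". It then fixes the count: "note edema and injection both have two reports each per slit-lamp examination". The same section assigns unscheduled visits to the nearest scheduled visit by day ranges (0–22, 23–45, 46–75, and 76 or later).

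Protocol Appendix B, Section 2.0, opens its list of scales with "The following parameters will be assessed during the Slit-Lamp Examination (without lenses"). Epithelial edema, epithelial microcysts and stromal edema follow as three separate scales, each graded 0 to 4. On the stromal scale, Grade 2 is "Mild: faint corneal striae (2 or fewer") and Grade 3 is "3 Moderate: pronounced corneal striae (3"). Grade 4 adds folds in Descemet's membrane.

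Protocol 6.1.1 to 6.1.4 and Appendix A schedule the slit-lamp examination at Screening/Dispensing and at the 2-Week, 1-Month, 2-Month and 3-Month visits. Appendix A also lists it for unscheduled visits, where assessments follow the Investigator's judgement. The Exit Visit column has no slit-lamp examination.

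**The concern.** A reader who meets a block headed as edema reports in a safety-trend table will take it as the table's account of corneal edema. As defined, the block covers epithelial edema and microcysts. An eye with stromal edema and neither of those findings shows nothing there.

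Unscheduled visits matter most here. The slit-lamp tables in SAP 4.9 are organised by scheduled visit, while the profile places unscheduled findings in a visit window. Protocol 6.1.6 provides these extra visits for subject safety and well-being, including for subjects with problems. A stromal finding at such a visit has no row in the table designed to locate it in time.

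What is at stake is the completeness of a descriptive table. No hypothesis, margin, sample size or success criterion depends on the profile.

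**Working it through.** This is a check of content, so the step is to count scales and set the two lists side by side.

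**1. The SAP's own count.** Scales named in the edema block: epithelial edema + epithelial microcysts = 2. This reproduces the two reports per examination in the closing note. The list and the note agree, so the omission is not damage from text extraction.

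**2. All graded findings.** Appendix B, Section 2.0, has ten finding scales graded 0 to 4, leaving aside the extra descriptors recorded for an infiltrate:

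| Appendix B scale (0–4) | Line in the SAP 4.8.2 profile |
|---|---|
| Epithelial edema | Yes, under edema |
| Epithelial microcysts | Yes, under edema |
| Stromal edema | **No** |
| Endothelial regularity | No |
| Corneal staining | Yes |
| Limbal injection | Yes, under injection |
| Bulbar injection | Yes, under injection |
| Upper lid tarsal abnormalities | Yes |
| Corneal neovascularization | Yes |
| Corneal infiltrates | Yes |

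The profile carries 8 of 10. Endothelial regularity has no natural heading in the profile. Stromal edema does, and is missing from it. Of the two scales named edema, the profile shows one.

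**3. Effect of adding stromal edema.** Reports per eye per examination go from 2 to 3. Over the four scheduled follow-up visits: 2 × 4 = 8 becomes 3 × 4 = 12. The count of two would then hold for injection only.

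**4. Volume of data with no line.** With all 680 planned eyes seen at all four visits: 680 × 4 = 2,720 stromal gradings. With the 600 eyes of 300 completing subjects: 600 × 4 = 2,400. These are gradings of any value, including 0, not positive findings.

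**5. Positive findings missed.** Not computable: neither document gives a stromal edema rate.

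**6. Where stromal edema still appears.**
- SAP 4.9, Slit-Lamp Examination: every category by grade at each scheduled visit, plus total findings of each grade across categories, by arm and by completion status.
- SAP 4.9, opening text: listings that include all visits, and a worst-across-visits measure for by-visit summaries.
- SAP 4.1.4 and 4.5.1: any graded finding above Grade 2 at a scheduled or unscheduled follow-up visit enters the primary safety endpoint.
- SAP 4.8.2: an event reported as a treatment-emergent adverse event enters the profile's adverse event total, though not as edema.

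**The case against.** The strongest reply is that this is a defined scope. The row names its two scales and the note repeats the number, so the SAP is consistent with itself. Appendix B describes the higher microcyst grades in terms of epithelial haziness, cloudiness and bullae, much as it describes epithelial edema. A block limited to the epithelium would therefore be coherent. Nothing says that the profile must carry every slit-lamp scale, and endothelial regularity is absent too. Stromal edema is tabulated by visit in SAP 4.9.

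Much of this stands. It rules out several stronger readings that a reader might infer:

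- *That the existing edema rows are wrong or under-count.* The wording points to separate counts for each named scale, and those counts would be correct for what they name. Only a pooled edema total would fall short, and the text does not clearly define one. Even then, the eye count would be short only for eyes with stromal edema and neither named finding.
- *That the omission is what stops the profile reconciling with the primary safety endpoint.* The SAP does not claim that the two reconcile. Adding stromal edema would not achieve it either, since an eye with only a Grade 3 endothelial finding would still have no slit-lamp line in the profile.
- *That one missed stromal event is a large share of the expected signal.* It is tempting to set one event against 0.008 × 300 = 2.4 eyes per arm (SAP 2.2.4). That figure is the expected number with any finding above Grade 2 on any scale. It is not an edema rate, so the ratio has no meaning here.
- *That the profile departs from the FDA guidance.* The guidance is not among the documents, so this cannot be judged.

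The reply does not explain why a block headed edema leaves out a scale named edema. Neither SAP 4.8.2 nor 4.10 gives a reason. The SAP 4.9 tables are also only a partial substitute, because they are by scheduled visit and do not use the profile's mapping of unscheduled visits.

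**Conclusion.** The point holds as a minor gap in a descriptive safety table. Stromal edema is graded at the screening and scheduled follow-up slit-lamp examinations but has no line in the Trend Analysis Profile, including for unscheduled findings that the profile maps to a visit window.

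The size is one scale of three under or next to the edema heading, missing from three rows at each of four visits and overall, in both arms. The 2,720 (or 2,400) gradings assume that every eye attends all four scheduled visits. The number of positive findings among them is unknown.

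The primary safety endpoint, the SAP 4.9 slit-lamp tables and the listings are unaffected, so no primary conclusion changes. The conclusion rests only on comparing the SAP with the protocol's grading scheme, and does not depend on the cited guidance.

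**What to change.** In SAP 4.8.2, extend the edema row so that it covers each of epithelial edema, epithelial microcysts and stromal edema. Change the closing note to three edema reports and two injection reports per slit-lamp examination.

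If the omission is intended, the alternative is to state the reason and relabel the block as epithelial edema and microcysts, so that nobody reads it as all corneal edema.

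The cost is one row definition, one note and one more block in an existing table. No new data are needed. SAP Section 1 says that the table formats were issued with V1 and not updated for V2, so that layout would need the same addition. Under the same section, a change made before database lock may need a SAP amendment, and one decided after lock is documented in the clinical study report.
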